7.2 General principle of statistics

The summary statistics will be presented with descriptive statistics including number of subjects, mean, standard deviation, median, minimum and maximum values for continuous variables. For categorical variables, number and percentage of subjects with event will be presented. For the test of significance between the two treatment groups, the two-sided test will be conducted at 5% significance level.

7.3 Analysis of demographic data and baseline characteristics

Demographic data and baseline characteristics will be summarized by treatment groups and overall. For continuous variables, the summary will be presented by number of subjects, mean, standard deviation, median, minimum and maximum value. For categorical variables, the summary will be presented by number and percentage of subjects in each category.

7.4 Efficacy Analysis

Efficacy analysis will be performed using the Full Analysis Set and Per-Protocol Set.

7.4.1 Primary Endpoint

Change in Hb levels from baseline to the evaluation period

Descriptive statistics will be provided by treatment group. The difference between treatment groups will be determined by ANCOVA (analysis of covariance) model with treatment as factor, and baseline Hb level and the change in weekly dosage per kg body weight from baseline to the evaluation period of Epodion® or Eprex® as covariates.

Therapeutic equivalence of Epodion® to the comparator Eprex® will be demonstrated if the two-sided 90% confidence interval of the difference of mean changes in Hb levels between treatment groups lay within the interval of ± 0.5 g/dL.

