1.3.1 Study Objectives

1.3.1.1 Efficacy Outcome

A. Primary Objectives

To demonstrate that the Epodion® treatment is equivalence to Eprex® by evaluating Hb level change between baseline and evaluation period.

B. Secondary Objectives

1. Obtain data mean change in weekly dosage per kg body weight between the baseline period and the evaluation period.
2. Calculating instability rate of Hb (hemoglobin) level during maintenance and evaluation period as defined when Hb (hemoglobin) level dropped below 8 g/dL or increase more than 13 g/dL.
3. Evaluating Hb (hemoglobin) and Hematocrit level during maintenance and evaluation period.

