2.4 Epodion®

Epodion® is an alpha rhEPO product produced by PT. Daewoong Pharmaceutical Company Indonesia. This product is used in conjunction with other clinical treatments for anemic patients due to chronic kidney disease or due to chemotherapy. Yellowish transparent Epodion® injection solution which can be injected intravenously or subcutaneously. Epodion® has four products with different EPO content, including 2000 IU, 3000 IU, 4000 IU, and 10000 IU.

At the beginning of Epodion® use, patients are given a dose of 50 units/kg of body weight three times a week which can be done intravenously or subcutaneously. If needed, the dose can be increased to 75 units/kg at 4-week intervals from the initial administration. If the increase in hemoglobin level increases by more than 2 gr/dL at the initial dose, the administration of Epodion® must be reduced to 2 times a week. Repair doses can be continued until the patient's hemoglobin level becomes 10 gr/dL. Anemia that has been overcome can be continued with a maintenance

dose of between 25 to 50 units/kg, 2 or 3 times a week. The expected hemoglobin range for treatment is 10-12 gr/dL. The initial hemoglobin level determines the treatment dose. In addition, the patient's age is also important in determining the dose. The dosage for the use of Epodion® should not exceed 200 units/kg and the frequency of administration is not more than 3 times a week. During treatment, the patient's iron levels need to be controlled. Chronic kidney failure patients who do not undergo hemodialysis, a dose of 70-150 units/kg per week is proven to maintain hematocrit levels 36-38% for more than 6 months.

Research on the effects of Epodion® on human bone marrow cell culture shows that Epodion® stimulates the formation of red blood cells and does not affect the formation of white blood cells. Animal studies using Epodion® showed in vivo efficacy in test animals. In addition, no cytotoxic effects were detected, changes in behavior, locomotor activity, circulation or breathing in test animals.

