3.2. Rationale Number of Subject

A sample size of 90 subjects will be determined with difference 0 g/dL, standard deviation 0.8 g/dL, statistical power 90%, randomization ratio 1:1 to demonstrate equivalence at 5% significance level and equivalence margin ± 0.5 g/dL. Assumption of difference and standard deviation for sample size estimation in this study was derived from PDA10 ITT set. Difference between treatment groups in PDA10 ITT set was -0.009, but this study assumed to be 0. Standard deviation 0.8 was an approximate estimation derived from two-sided 90% confidence interval [-0.189, 0.171]. After an assumption of 10% drop-out rate for this trial, about 100 subjects will be enrolled to the trial. The sample size calculated using the POWER procedure (Proc Power procedure) of SAS ver. 9.4 (SAS Institute, Cary, NC, USA).

```

*****
+ PROGRAM NAME. : SAS Proc Power_EPO.sas
+ OUTPUT : EPO_Biosimilar_Sample Size_20191014.pdf
+ SAS VERSION : SAS 9.4
+ FIRST DATE : 14 Oct 2019
+ WRITTEN BY : DW Randomization Statistician
+ COMMENTS : Sample Size Calculation & Power for EPO_Biosimilar
+ : Reference: PDA10 Study
*****

proc power;
  twosamplemeans test=equiv_add
  lower = -0.5
  upper = 0.5
  meandiff = 0
  stddev = 0.8
  groupweights = (1 1)
  ntotal = .
  power = 0.9;
run;

```

Figure 4. SAS code used in determining study subject number

Figure 5. SAS output

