4.4.6 Dose Information

Doses must be individualized to ensure that hemoglobin is maintained at an appropriate level for each subject. Screening period initials dose 50 IU/Kg body weight three times per week. During titration, titrated dose closely to achieve baseline Hb level 10-12g/dL. In maintenance period administer Eprex® and Epodion® equal previous stable dose in titration period. Dose is allowed to be increased or decreased during maintenance period at an appropriate level according to the condition of the subject.

CHAPTER 5. SELECTION OF SUBJECTS AND DROPOUT CRITERIA

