5.4 Temporary Discontinuation

If the following situation occurs, the investigator shall delay investigational product administration until the situation will be settled. Then, investigational product administration shall be delayed to the extent of investigational product administration schedule indicated.

The following condition when investigational product should be delayed are detailed below:

- Increase blood pressure systole ≥ 180 mmHg and/or diastole ≥ 120 mmHg.
- Hb level exceed 13 g/dL, investigational product should be reinitiated at approximately 25% lower than the previous dose after haemoglobin levels fall to 12 g/dl (7.45 mmol/l) or below.
- Any reason based on the assessment of the principal investigator.

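### The primary ANCOVA adjusts for dose change after randomisation, so it estimates the Hb difference named in the equivalence rule only if dose changes match between arms or the within-arm slope is zero

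*Protocol*

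**What the plan says.** Protocol 7.4.1 and SAP 3.1 specify the same primary model. The between-arm difference comes from an ANCOVA with treatment as factor and two covariates: baseline Hb and "the change in weekly dosage per kg body weight from baseline to the evaluation period of Epodion® or Eprex® as covariates". Equivalence is then judged on "the two-sided 90% confidence interval of the difference of mean changes in Hb levels between treatment groups", which must lie within ±0.5 g/dL. The primary objective (protocol 1.3.1.1) is "To demonstrate that the Epodion® treatment is equivalence to Eprex® by evaluating Hb level change between baseline and evaluation period". It does not mention holding dose change equal.

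Patients are randomised after the baseline evaluation period (protocol 4.4.3). From then on the dose may be raised or lowered to keep Hb at 10-12 g/dL (protocol 6.2). One rule in protocol 5.4 ties dose directly to the outcome: "Hb level exceed 13 g/dL, investigational product should be reinitiated at approximately 25% lower than the previous dose". The same section also allows treatment to be delayed for blood pressure or for any reason the investigator judges sufficient. The between-arm comparison of dose change is the first secondary endpoint (protocol 7.4.2(1)), with no margin.

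The sample size (protocol 3.2) rests on "A sample size of 90 subjects will be determined with difference 0 g/dL, standard deviation 0.8 g/dL, statistical power 90" per cent. Its SAS code is "twosamplemeans test=equiv_add", a comparison of two means without covariates.

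**The concern.** A covariate that treatment can affect is not a baseline characteristic. Adjusting for it changes the quantity being estimated. If the two products need different doses to hold the same Hb, dose change carries part of the treatment difference, and the model removes some of that difference or adds to it. The single confirmatory decision rests on this coefficient. No inferential model without the dose term is planned, and the FAS analysis uses the same model as the PPS. The adjustment matters when the products differ in dose need, which is a difference an equivalence trial should not obscure.

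**Working it through.** **Planning figure first.** Inputs from protocol 3.2: difference 0, SD 0.8, margin 0.5 g/dL, 5% per side, no covariate. Exact two one-sided test power is 80.5% at 45 per arm and 85.5% at 50. The stated 90% needs 57 per arm. The drop-out step reproduces: 90 / (1 - 0.10) = 100. The power shortfall is a separate finding and carries no weight here. What matters for this point is that the calculation is for a difference in means with no dose adjustment.

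**Identity.** For the least-squares fit,

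adjusted difference = τ - b × d

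- τ is the arm difference in Hb change adjusted for baseline Hb only.
- b is the pooled within-arm slope of Hb change on dose change, given baseline Hb.
- d is the arm difference in dose change (Epodion minus Eprex), adjusted for baseline Hb.

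The identity held to rounding in a generated data set (0.28149 both ways). The shift is zero only if b = 0 or d = 0.

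**Assumed sizes.** The documents give no b, no d and no SD of dose change. They do give a dose scale: "dose of between 25 to 50 units/kg, 2 or 3 times a week" (protocol 2.4) and "Screening period initials dose 50 IU/Kg body weight three times per week" (protocol 4.4.6). The weekly range is 25 × 2 = 50 to 50 × 3 = 150 IU/kg. An assumed 20% arm difference is then d = 10 to 30 IU/kg/week. Assumed slopes are -1.0, -0.5, -0.2 and +0.5 g/dL per 100 IU/kg/week, and the assumed SD of dose change is 40 IU/kg/week.

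Example: with τ = -0.50, b = -0.010 and d = 30, the adjusted difference is -0.50 - (-0.010 × 30) = -0.20.

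**Simulation.** 45 per arm, SD of Hb change 0.8, true difference -0.50, 90% CI rule. Without the dose covariate, equivalence is declared in about 5% of trials in every row.

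| Slope per 100 IU/kg/week | d = 10: estimate, share declared equivalent | d = 30: estimate, share declared equivalent |
|---|---|---|
| -1.0 | -0.40, 16.5% | -0.20, 59.2% |
| -0.5 | -0.45, 8.8% | -0.35, 21.1% |
| -0.2 | -0.48, 6.3% | -0.44, 9.4% |
| +0.5 | -0.55, 2.7% | -0.65, 0.6% |

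Reversing d reverses every shift. With d = -30 and slope -1.0 the estimate is -0.50 - 0.30 = -0.80, and the share is below 0.1%.

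The error also runs the other way. With a true difference of 0 and d = 30, equivalence is declared in 35.0%, 60.4%, 69.8% and 60.5% of trials (slopes in table order), against 80% without the covariate. With b = 0 or d = 0, the rule holds its 5% at the margin.

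**Precision given up by dropping the covariate** (true difference 0, equal dose need, raw SD 0.8). At dose-change SD 40, power with and without the covariate is 91.2% and 79.9% at slope -1.0, and within 3 points at the other slopes. At SD 60 and slope -1.0 it is 99.4% and 79.9%.

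If 0.8 is instead a dose-adjusted SD, the raw SD is √(0.8² + (b × dose-change SD)²):

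- SD 40, slope -1.0: √(0.64 + 0.16) = 0.89. Over the four slopes, power without the covariate is 68-80% at 45 per arm.
- SD 60, slope -1.0: √(0.64 + 0.36) = 1.00, and power is 52%.

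**The case against.** The strongest defence is that protocol 7.4.1 says the difference is determined by the ANCOVA, so the rule may mean the dose-adjusted difference. For that quantity the 90% interval keeps its nominal level. This stands in part: the error-rate statement holds only if the target is the Hb difference not conditioned on dose. The documents define no dose-adjusted target, and the objective, the rule's wording and the sample size all point to the unconditional difference. Nor does regression on an Hb-driven dose recover Hb at a fixed dose, because the slope mixes drug effect with the response of dose to Hb.

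It is also fair that every size above is assumed. The protocol hypothesises equivalence, and with equal dose need there is no bias. An arm difference of 30 against an SD of 40 is a gap of 0.75 SD, so the 59% is an edge of the grid. Descriptive statistics by arm would let a reader build an unadjusted interval, and a dose-change comparison is already planned. Both soften the problem, but neither enters the decision.

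A reader might infer that the covariate pushes the trial towards equivalence. The documents do not support that. Hb-driven titration tends to make the slope negative, but holds for other reasons can push it the other way, and the sign of any dose difference is unknown.

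**Conclusion.** The mismatch is structural and certain; its size is not. The planned coefficient matches the Hb difference in the objective and rule only if dose changes match between arms or the slope is zero. If neither holds and the target is not conditioned on dose, equivalence can be declared too often or too rarely. The illustrated shares (about 3-17% at a dose difference of +10, below 0.1% to about 59% at 30 in either direction, against 5%) rest on assumed slopes, dose differences and a dose-change SD of 40. The 3-17% covers one direction only; with the difference reversed, the lower end would be smaller.

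A reader might go further and conclude that this trial's error rate is in fact broken, or that the result will be biased. The documents give no slope or dose difference, so they do not show that. Because the sole confirmatory decision uses this coefficient, the model should still be changed.

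**What to change.** In protocol 7.4.1 and SAP 3.1, make the single primary model an ANCOVA with treatment as factor and baseline Hb as the only covariate, in both the PPS and the FAS. Leave the 90% interval and the ±0.5 g/dL rule unchanged. Move the model with dose change to a labelled sensitivity analysis. Report the arm difference in dose change already planned in protocol 7.4.2(1) with a 90% CI beside the Hb result. This is for interpretation only, because no dose margin is stated.

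The cost is a short amendment, approved as protocol 9.2 requires, with no new data. With 0.8 as the raw SD and equal dose need, power falls by 0-11 points at dose-change SD 40 and by up to about 19 at SD 60. The sample size never counted that gain. Protocol 3.2 does not say which model its SD came from. If it is a dose-adjusted SD, the lower power figures in the working apply (68-80%, or as low as 52%).

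The change removes only the bias from this covariate. Titration still pulls Hb together under either model, and the PPS and FAS both still select patients after randomisation.

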7.4.2 Secondary Endpoint

(1) Change in weekly dosage per kg body weight from baseline to the evaluation period.

Descriptive statistics will be provided treatment group. The difference between treatment groups will be analyzed by ANCOVA model with treatment as factor, and baseline Hb level and baseline weekly dosage per kg body weight value as covariates.

(2) Instability rate of Hb level during maintenance and evaluation period

The number of subjects with Hb level <8 g/dl or Hb level >13 g/dl during maintenance and evaluation period will be provided by treatment groups along with rates and the two-sided 95% confidence intervals. Also, the difference in the rates between the treatment groups and two-sided 95% confidence interval will be provided.

(3) Hb and Hematocrit level during maintenance and evaluation period

Descriptive statistics will be provided treatment groups for Hb and Hematocrit levels at baseline and at each bi-week during maintenance and evaluation period. The time course figure of Hb levels will be presented using mean and standard deviation throughout maintenance and evaluation period.

7.5 Safety Analysis

Safety analysis will be performed using the Safety Set.

(1) Adverse events (AEs)

The incidence of the following events will be summarized by treatment group for all observed adverse events, local reactions and systemic reactions.

- Treatment-emergent adverse events (TEAEs)
- Adverse Drug Reactions (ADRs)
- Serious TEAEs/ADRs
- TEAEs/ADRs leading to investigational product discontinuation
- TEAEs/ADRs leading to death

(2) Vital sign, Laboratory test

Summary statistics for change from baseline in vital signs and the laboratory test evaluation will be provided. Clinically significant abnormal results in laboratory test will

also be summarized. If needed, laboratory re-tests may be carried out outside the schedule to monitor the patient's condition.

7.6 Handling of dropout or missing values

Analysis for efficacy variables will be performed for subjects who have at least 1 Hb level for the evaluation period. For by visit analysis (ANCOVA, Hb and Hematocrit level), missing data will be imputed by LOCF (last observation carried forward) method. For calculating the instability rate, only observed data will be used. For safety analysis, no imputation will be made for missing data.

CHAPTER 8. ADVERSE EVENTS

8.1 Definition of Adverse Event

a. Adverse event (AE)

Any untoward medical occurrence in a patient or subject administered a pharmaceutical product and which does not necessarily have a causal relationship with this treatment. An adverse event (AE) can therefore be any unfavorable and unintended sign (including an abnormal laboratory finding), symptom, or disease temporally associated with the use of a medicinal (investigational) product, whether or not related to the medicinal (investigational) product (see the ICH Guideline for Clinical Safety Data Management: Definitions and Standards for Expedited Reporting).

b. Adverse Drug Reaction (ADR)

In the pre-approval clinical experience with a new medicinal product or its new usages, particularly as the therapeutic dose(s) may not be established: all noxious and unintended responses to a medicinal product related to any dose should be considered adverse drug reactions. The phrase responses to a medicinal product means that a causal relationship between a medicinal product and an adverse event is at least a reasonable possibility, i.e., the relationship cannot be ruled out.

Regarding marketed medicinal products: a response to a drug which is noxious and unintended and which occurs at doses normally used in man for prophylaxis, diagnosis, or therapy of diseases or for modification of physiological function (see the ICH Guideline for Clinical Safety Data Management: Definitions and Standards for Expedited Reporting).

c. Serious Adverse Event (SAE) or Serious Adverse Drug Reaction (SADR)

Any untoward medical occurrence that at any dose:

1. Results in death
2. Is life-threatening
3. Requires inpatient hospitalization or prolongation of existing hospitalization
4. Results in persistent or significant disability/incapacity, or
5. Is a congenital anomaly/birth defect

d. Unexpected Adverse Drug Reaction

It means that there is a difference in the aspect or risk of adverse drug reaction in view of available medication information such as from IB, insert paper or label.

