The time needed to reach maximum concentration in uremia patients averages 12-28 hours with subcutaneous administration. The bioavailability of Epodion® by subcutaneous administration is 23-42% compared with intravenous administration. Half-life of Epodion® given intravenously to healthy volunteers and kidney failure patients ranges from 4-12 hours with a distribution volume reaching 1 to 2 times the plasma volume. This is similar to the results found in studies in mice with uremia and normal mice. The half-life of the terminal Epodion® by subcutaneous administration in uremia patients averages 13-28 hours, longer than intravenous administration.

The most common side effect is hypertension or worsening hypertension. This increase in blood pressure can be treated with antihypertensive agents. If the hypertension that occurs cannot be overcome with anti-hypertensive drugs, it is recommended to temporarily stop giving Epodion®. Therefore, it is recommended to monitor the possibility of a hypertensive crisis with symptoms resembling encephalopathy (eg, headache, confusion, sensorimotor disorders, tonic clonic (seizures), including in patients with normal or low blood pressure.

In addition, leukocytosis, eosinophilia can sometimes occur. Granulocytopenia can sometimes occur in premature infants. Increases in serum potassium, BUN, creatinine and gout have been reported to occur occasionally. Although rare, thrombocytosis can occur. Reported red cell hypoplasia after administration of Epodion® product in patients with chronic kidney failure from several months to several years is rare. In addition, there may be an increase in platelet counts during Epodion® therapy, especially if given IV. This increase in platelet counts associated with the dose of Epodion® given is usually within normal limits and will improve if Epodion® therapy is given. The incidence of thrombocytosis is very rare. However, it is recommended to monitor platelet levels during the first 8 weeks of Epodion® therapy.

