Often, a higher dose of heparin is needed during hemodialysis due to an increase in hematocrit levels. In addition, a dialysis system blockage may occur if heparinization is not optimal. Shunt thrombosis can occur in patients who tend to be hypotensive or patients with complications of the arteriovenous fistula (eg, aneurysm, stenosis). In these patients it is recommended to give thrombosis prophylaxis to administration of acetalsalate. In some patients, there is a decrease in serum ferritin levels together with an increase in hematocrit. For this reason, it is recommended to provide 200 mg / day of oral iron (Fe²⁺) substitution in patients with serum ferritin levels <100 ug / L or transferrin saturation <20%. Then, there is a temporary increase in serum potassium and phosphate levels. Therefore, it is recommended to monitor these parameters regularly.

CHAPTER 3. STUDY DESIGN OVERVIEW

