6.4.2 Contraindications

Epodion is contraindicated in patients with the following conditions:

- a. Hypersensitivity to other drugs or Erythropoietin products
- b. Patients who develop pure red cell aplasia (PRCA) following treatment with any erythropoietin
- c. Uncontrolled hypertension
- d. Hypersensitivity to derivative products from mammalian cells or albumin
- e. Patients experience events that result in severe damage to coronary, peripheral, carotid or cerebral vessels.
- f. Patients scheduled to follow any surgery who for any reason cannot receive adequate antithrombotic prophylaxis or treatment

CHAPTER 7. STATISTICAL ANALYSIS PLAN

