8.4 Reporting of Serious Adverse Events

The investigator should report any serious adverse events (SAEs) in the study immediately to sponsor and Ethics Comitee. The definition of a serious adverse event is a medical event which at any dose takes the form of:

- a. Results in death
- b. Is life-threatening
- c. Requires inpatient hospitalization or prolongation of existing hospitalization
- d. Results in persistent or significant disability/incapacity
- e. A congenital anomaly/birth defect.

All SAEs above are reported to the sponsor no later than 24 hours since they are known and reporting to the ethics committee a maximum of 3 calendar days since they are known. Sponsors must report to the regulatory authority no later than 7 calendar days from the time it is first known (for the occurrence of death), 15 days for other serious adverse events. In this study the investigator immediately contacts the safety report and provides further and detailed reporting through.

[contact]

E-mail: [contact]

CHAPTER 9. ETHICAL CONSIDERATIONS AND ADMINISTRATIVE PROCEDURES

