##### **3.3.1.1. Treatment-emergent adverse events (TEAEs)**

##### **3.3.1.2. Adverse Drug Reactions (ADRs)**

##### **3.3.1.3. Serious TEAEs/ADRs**

##### **3.3.1.4. TEAEs/ADRs leading to investigational product discontinuation**

##### **3.3.1.5. TEAEs/ADRs leading to death**

#### **3.3.2. Vital sign, Laboratory test**

Summary statistics for change from baseline in vital signs and the laboratory test evaluation will be provided. Clinically significant abnormal results in laboratory test will also be summarized. If needed, laboratory re-tests may be carried out outside the schedule to monitor the patient's condition.

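### The serious-adverse-event definition has no criterion for important medical events, so red-cell aplasia or shunt thrombosis managed without admission could miss expedited reporting and the serious-event row

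*Protocol*

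**What the plan says.** Protocol 8.1c lists five criteria for a serious event. The first is "Results in death" and the third is "Requires inpatient hospitalization or prolongation of existing hospitalization"; the others are a threat to life, lasting or marked disability, and a birth defect. Protocol 8.4 repeats the same five and attaches the reporting clock to them: "All SAEs above are reported to the sponsor no later than 24 hours since they are known". The same section gives 3 calendar days for the ethics committee. The sponsor has 7 calendar days to inform the regulator of a death and 15 days for other serious events.

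Protocol 7.5 and SAP 3.3.1.3 both plan a by-arm summary of "Serious TEAEs/ADRs". The SAP does not define the term serious.

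The protocol also names specific product risks. Section 2.4 includes "Reported red cell hypoplasia after administration of Epodion® product in patients with chronic kidney failure", which it calls rare. It recommends that staff "monitor the possibility of a hypertensive crisis with symptoms resembling encephalopathy", and it says "Shunt thrombosis can occur in patients who tend to be hypotensive" or who have fistula complications. Section 6.4.2 lists as a contraindication "Patients who develop pure red cell aplasia (PRCA) following treatment with any erythropoietin".

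**The concern.** A definition built only on these five outcomes leaves out an event that is clinically important but was contained before it reached one of them. That matters here because the protocol identifies risks of that kind, and because the setting makes management without admission plausible. Subjects are dialysed at the hospital site (synopsis, study population) three times a week (1.4), and haemoglobin is measured every two weeks during maintenance (4.4.4).

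Prompt notification and correct classification are at stake. An event below the serious threshold reaches the sponsor only through the periodic reporting in 9.4. The sponsor's power to withdraw the study in 9.10 depends on learning of critical safety information. Serious events are a stated safety outcome (1.3.1.1, Safety Outcome), and the hypothesis in 1.3.2 extends to safety. The serious-event row is therefore one that readers will look at.

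**Working it through.** No arithmetic applies. The check compares the two definitions, looks for any other route, follows what depends on the serious flag, and tests the named risks against the list.

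1. *Are the two lists the same and closed?* All five items in 8.1c reappear in 8.4. In 8.1c the conjunction before the fifth item ends the list. Neither list has a sixth item or a clause for medical judgement.

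2. *Does anything else fill the gap?* Neither document has a list of events of special interest or a second expedited route. The severity scale in 8.3.1 is separate and triggers no report. Section 8.2 asks the investigator to assess an event's significance, but does not define that or link it to reporting. The ICH guideline is cited under 8.1a and 8.1b but not under 8.1c, so the citation does not supply the missing criterion.

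3. *What depends on the flag?* The sponsor, ethics and regulatory reports in 8.4, and the serious-event summary in protocol 7.5 and SAP 3.3.1.3.

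4. *How do the named risks fare if managed without admission?*

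| Named risk | Where named | Criterion that could still apply |
|---|---|---|
| Red-cell hypoplasia or aplasia | 2.4, 6.4.2 | None, unless judged life-threatening or disabling |
| Shunt thrombosis | 2.4 | None, unless judged life-threatening or disabling |
| Hypertensive crisis with encephalopathy-like symptoms | 2.4 | Threat to life is a ready classification, especially with seizures |

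5. *What happens to an event that meets none of the five?*

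| Kept | Missed |
|---|---|
| CRF record (8.2) | 24-hour sponsor report |
| Treatment-emergent event table | 3-day ethics report |
| Drug-reaction table, if judged related | Regulatory report |
| Discontinuation table, if treatment stops | Serious-event row |

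**The case against.** The strongest reply is that nothing in the documents is contradicted. The two lists agree with each other and with the reporting clocks, and the documents contain no rule that requires a sixth criterion. That stands: this is an improvement to a design choice, not an internal error.

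It can also be said that the gap is narrow. The documents call red-cell hypoplasia rare and place its onset after several months to several years, whereas randomised treatment lasts 24 + 4 = 28 weeks with 50 subjects per arm. Section 2.4 ties shunt thrombosis to patients who tend to be hypotensive or have fistula complications. No passage says that any of these events would be managed without admission; that is inferred from the setting. This limits how often the gap would matter, but does not close it.

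A reader might infer that these events would disappear from the safety data. The documents do not support that, because the CRF record and the other tables remain. A reader might also infer that a hypertensive crisis with seizures would be classed as non-serious. The life-threatening criterion could readily cover it, so this is a weaker example than the other two. Nor is it right that the serious flag simply tracks admission practice: four of the five criteria do not mention admission.

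**Conclusion.** The point holds in a limited form. As written, the definition would leave an important event non-serious if it was managed without admission and judged neither life-threatening nor disabling. The clearest cases are red-cell hypoplasia or aplasia and shunt thrombosis. The loss is expedited notification and the entry in one row of the safety table; the event itself is not lost. The primary equivalence conclusion is untouched.

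The size cannot be given as a number. One might try to express it as a single event among 50 in an arm, which is 1/50 = 2%. That figure describes any one event in any table, presumes a starting count of zero and does not measure this gap. The documents give no incidence for these events in this population.

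The conclusion rests on two assumptions: that some such events would be handled without admission, and that investigators would apply the list as written. The change is still worth making, because it is cheap and improves the reporting of risks that the protocol has already identified.

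**What to change.** Add a sixth criterion to both 8.1c and 8.4, for example: *is an important medical event that, in medical judgement, may jeopardise the subject or require intervention to prevent one of the outcomes above*. Name red-cell hypoplasia or aplasia, shunt thrombosis and hypertensive crisis as examples to be considered under it. In SAP 3.3.1.3, state that serious has the meaning given in protocol 8.1c. Update the SAE form to match.

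Do not make every access thrombosis or hypertensive crisis serious automatically. That would replace the judgement that the criterion relies on, and would put events that put no one at risk of a listed outcome into the serious row.

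The cost is a few sentences and a form change, a few more expedited reports, and possibly a slightly higher stated serious-event rate. The change concerns classification and reporting only and leaves dosing and patient care as they are.
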